7.5.4 Laboratory parameters

The descriptive statistics for laboratory data collected at each visit and changes from Baseline will be provided.

A summary table of the categorical grade shift changes using the normal ranges from baseline to the last post-baseline visit will be presented for each laboratory parameter. Only SAF subjects with both baseline and post-baseline assessments will be included in this analysis.

For each laboratory test, a complete data listing will be provided for subjects who have any laboratory results outside the reference ranges, and for subjects who have any laboratory results with clinical significance.

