3.2.3 Laboratory safety tests

The laboratory analyses will be based on Central laboratory results. The following laboratory safety tests will be performed at the Screening visit, Week 26 and Week 52/ET visits. Abnormal laboratory results will be evaluated by the investigator as clinically significant or non-clinically significant.

- Hematology: White blood cell (WBC) count with differential, red blood cell (RBC) count, hemoglobin(Hb), hematocrit (Hct), mean cell volume (MCV), and platelet count (Plt)
- Blood chemistry: Creatinine, uric acid, urea nitrogen, gamma glutamyl transferase (GGT or γ GTP), alkaline phosphatase (ALP), aspartate aminotransferase (ASAT=SGOT [AST in US]), alanine aminotransferase (ALAT=SGPT [ALT in US]), and bilirubin (total, direct & indirect).
- Urinalysis: blood, proteins, leukocytes, glucose

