7.5.2 Cutaneous safety

Analyses of the local tolerability on the face will be based on SAF population; and the analyses of the local tolerability on the trunk will be based on SAFT population.

Local tolerability variables (erythema, scaling, dryness, stinging/burning) will be summarized at Baseline, each post-baseline visit, "Worst" score, and "Final" score. "Worst" score is the highest severity score observed during post-baseline period for a subject. "Final" score is the last data observed during the post-baseline period for a subject. In addition, the number and percentage of subjects with a local tolerability score worsened from baseline will be summarized descriptively at each post-baseline visit, "Final" scores, and "Worst" score.

Additionally, subjects with a local tolerability score worse than the Baseline score will be summarized graphically at each post-Baseline visit including "Final" scores and "Worst" score.

Summary statistics by treating the severity scale as continuous outcome will also be presented.

Subgroup analyses by Age Group (<18 years, >=18 years), Race (white, non-white), Gender (female, male), Country (Europe, USA), and Skin Phototype (I-III, IV-VI) will be provided.

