7.9 Analysis visit definition

For efficacy, DLQI/ C-DLQI and local tolerability data, analysis visit will be assigned according to the algorithm in Table 3 below to summarize the data by proper visit window interval. Study day is calculated as visit date minus the date of first application plus 1. If multiple measurements are taken in the same interval, the one closest to the target study day will be used for the analysis. If two measurements are taken with equal differences in timing compared with the target date, the nominal visit number (recorded on the CRF page) will be used. If there is missing measurement at Baseline, Screening data will be used to impute the missing baseline data, i.e. Baseline will be the last available data prior to first application of study drug.

Table 3 Analysis Visit and Visit Window

Analysis Visit	Analysis Visit Number in Derived Dataset	Target Study Day	Visit Window (Study Day)
Baseline	1	1	[≤1]
Week 1	2	8	[2 – 11]
Week 2	3	15	[12 – 21]
Week 4	4	29	[22 – 42]
Week 8	5	57	[43 – 70]
Week 12	6	85	[71 – 112]
Week 20	7	141	[113 – 161]
Week 26	8	183	[162 – 224]
Week 38	9	267	[225 – 315]
Week 52	10	365	> 315

When assigning the analysis visits for vital signs, no visit window will be applied; Nominal eCRF visit will be used as analysis visit for summaries. Only data from schedule visit will be summarized.

When assigning the analysis visits for laboratory data, no visit window will be applied, however, the following rules will be applied:

1. If sample date is at or prior to date of first application, the data will be considered as screening visit. If multiple measurements of screening due to rescreening, retest or other unexpected reasons, the data closest to date of first application will be chosen.
2. Lab data from scheduled visit will be considered first when assigning analysis visit of each scheduled visit. If there is no data from scheduled visit available, the last of those corresponding unscheduled visit will be considered for assignment of analysis visits.
3. When assigning Final visit, the lab data from the last post-baseline scheduled visit during treatment period will be considered first. If the last scheduled visit during treatment period have missing lab data due to any reason and there are subsequent unscheduled lab data available, the last of those corresponding unscheduled lab data will be assigned as Final visit. Otherwise, the previous visit lab data will be considered in the same manner.

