- Summary of Adverse Events by System Organ Class and Preferred Term by Skin Phototype, SAF Population
- Summary of chronology of Adverse Events, SAF Population
- Summary of Erythema on the Face, SAF Population
- Summary of Scaling on the Face, SAF Population
- Summary of Dryness on the Face, SAF Population
- Summary of Stinging/Burning on the Face, SAF Population
- Summary of Erythema on the Trunk, SAFT Population
- Summary of Scaling on the Trunk, SAFT Population
- Summary of Dryness on the Trunk, SAFT Population
- Summary of Stinging/Burning on the Trunk, SAFT Population
- Summary of Erythema Worse than Baseline on the Face, SAF Population

- Summary of Scaling Worse than Baseline on the Face, SAF Population
- Summary of Dryness Worse than Baseline on the Face, SAF Population
- Summary of Stinging/Burning Worse than Baseline on the Face, SAF Population
- Summary of Erythema Worse than Baseline on the Trunk, SAFT Population
- Summary of Scaling Worse than Baseline on the Trunk, SAFT Population
- Summary of Dryness Worse than Baseline on the Trunk, SAFT Population
- Summary of Stinging/Burning Worse than Baseline on the Trunk, SAFT Population
- Summary of Erythema Worse than Baseline on the Face by Gender, SAF Population
- Summary of Scaling Worse than Baseline on the Face by Race, SAF Population
- Summary of Dryness Worse than Baseline on the Face by Age, SAF Population
- Summary of Stinging/Burning Worse than Baseline on the Face by Country, SAF Population
- Summary of Erythema Worse than Baseline on the Trunk by Gender, SAFT Population
- Summary of Scaling Worse than Baseline on the Trunk by Race, SAFT Population
- Summary of Dryness Worse than Baseline on the Trunk by Age, SAFT Population
- Summary of Stinging/Burning Worse than Baseline on the Trunk by Country, SAFT Population
- Listing of Central Laboratory Data Normal Ranges
- Summary of Laboratory Data - Hematology, SAF Population
- Summary of Laboratory Data - Blood Chemistry, SAF Population
- Summary of Laboratory Data - Urine Drug Screen, SAF Population
- Shift table of Laboratory Data from Baseline to last visit - Hematology, SAF Population
- Shift table of Laboratory Data from Baseline to last visit - Blood Chemistry, SAF Population
- Shift table of Laboratory Data from Baseline to last visit - Urine Drug Screen, SAF Population
- Listing of subjects with Laboratory Data Out of Reference Range, SAF Population
- Listing of subjects with Clinical Significant Laboratory Data, SAF Population

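### Laboratory shifts run only to the last value, with scheduled samples taking precedence, so no planned table counts subjects with any on-treatment out-of-range result

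*SAP*

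**What the plan says.** - **Sampling.** SAP 3.2.3: "The following laboratory safety tests will be performed at the Screening visit, Week 26 and Week 52/ET visits". A subject who completes therefore has two scheduled post-baseline samples.
- **Shift table.** SAP 7.5.4 plans a categorical shift "from baseline to the last post-baseline visit will be presented for each laboratory parameter". The table list in section 9 agrees, for example "Shift table of Laboratory Data from Baseline to last visit - Hematology, SAF Population", with matching entries for the other two panels. It contains no shift by visit and none to a worst value.
- **By-visit statistics.** SAP 7.5.4: "The descriptive statistics for laboratory data collected at each visit and changes from Baseline will be provided".
- **Choice of value.** SAP 7.9, rule 2: "Lab data from scheduled visit will be considered first when assigning analysis visit of each scheduled visit", and "If there is no data from scheduled visit available, the last of those corresponding unscheduled visit will be considered for assignment of analysis visits". For the Final visit, rule 3 says that "the lab data from the last post-baseline scheduled visit during treatment period will be considered first". A later unscheduled result is used only if that scheduled sample has no laboratory data.
- **Other outputs.** SAP 7.5.4 plans listings of subjects with any out-of-range result and of subjects with any clinically significant result. SAP 7.5.3 makes out-of-range results that are both clinically significant and drug-related AESIs, tabulated by system organ class and preferred term.
- **Comparison.** For local tolerability, SAP 7.5.2 plans a worst score as well as a final one; the worst "score is the highest severity score observed during post-baseline period for a subject".

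**The concern.** The primary objective is long-term safety and SAP section 7 plans no inferential analysis, so the descriptive safety tables are the evidence. A basic question for laboratory safety is how many subjects had a result outside the normal range at any time on treatment. The only table that classifies change against the normal range looks at one post-baseline value per subject. The rules that select that value do not look for the most abnormal one. A transient abnormality, or one found only at an unscheduled sample, is then not counted. A reader who takes the shift table as the frequency of on-treatment abnormality would read too low a figure, and the error can run only in that direction.

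**Working it through.** The plan gives no figure to reproduce. The check has two parts: tracing which results reach which output, and an illustration of size under stated assumptions.

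**Tracing the rules.** Take a subject who is normal at baseline, and read the last visit in 7.5.4 as the Final visit of 7.9, rule 3.

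| Pattern | Shift table | By-visit statistics | Out-of-range listing |
|---|---|---|---|
| Week 26 out of range, Week 52 normal | No shift | Yes, at Week 26 | Yes |
| Unscheduled result out of range; scheduled results present and normal | No shift | No | Yes |
| Week 52 out of range | Shift | Yes, at Week 52 | Yes |
| Last scheduled sample missing; last later unscheduled result out of range | Shift | Yes, in place of the missing one | Yes |

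The first two rows are the gap. By-visit statistics for continuous variables are means, medians, standard deviations, minima and maxima (SAP section 7). They can show an extreme Week 26 value but not how many subjects left the normal range. Urinalysis results recorded as categories would have frequencies at each visit, but these still do not combine into a count per subject. The listings show the values without a numerator or denominator, and 7.5.4 does not restrict them to post-baseline results. The AESI table counts subjects, but only for results that pass two investigator judgements.

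**Size, by assumption.** The SAP gives no abnormality rates. Consider subjects with both scheduled samples, ignore unscheduled ones, and let:

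- p = probability of an out-of-range result at each of the two visits (assumed equal)
- r = probability that a Week 26 abnormality is still present at Week 52

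Then:

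- ever abnormal = p + p − pr = p(2 − r)
- abnormal at the last visit = p
- missed = p(2 − r) − p = p(1 − r)
- missed share of the ever-abnormal = (1 − r)/(2 − r)

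With numbers:

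- r = 1 (all persist): 0/1 = 0%
- r = 0.8: 0.2/1.2 = 17%
- r = 0.5: 0.5/1.5 = 33%
- Independent samples (r = p), ever abnormal = 1 − (1 − p)²:
  - p = 2%: 3.96% ever against 2% at last visit; missed 1.96/3.96 = 49%
  - p = 5%: 9.75% against 5%; missed 4.75/9.75 = 49%
  - p = 10%: 19% against 10%; missed 9/19 = 47%

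For a fixed r the share does not depend on p. Low prevalence matters only at the independent end, where r equals p and the share approaches one half as p falls.

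**The case against.** The strongest reply is that nothing is misstated. Sections 7.5.4, 7.9 and 9 agree with each other, and the table is labelled as a shift to the last visit. It describes status at the end of observation and is not biased for that. This stands: the point is a missing table, not an error in the planned one.

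A reader might infer that transient or unscheduled abnormalities disappear from the safety reporting altogether. The document does not support that. Scheduled Week 26 values stay in the by-visit statistics, both listings cover any qualifying result whether scheduled or not, and the AESI table does not depend on the visit rules. What is absent is a count of subjects for abnormalities not judged both clinically significant and related.

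A reader might also infer that about half of affected subjects are missed. That figure needs independent samples. With full persistence none is missed, and a subject who leaves before Week 26 has only the early-termination sample, so no earlier scheduled value is lost. Nor does the SAP say that unscheduled post-baseline samples are drawn for cause; they may be repeat tests.

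The contrast with local tolerability is suggestive only. That scale runs in one direction and is scored at every post-baseline visit, whereas laboratory values can deviate high or low and have two scheduled post-baseline samples. Finally, an ever-abnormal count rises with the number of samples, and this study has no control arm to read it against. That is a real limit on interpretation, but not a reason to leave the count out.

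**Conclusion.** The concern holds in a limited form. The only laboratory summary that classifies change against the normal range uses the last post-baseline value, and scheduled results take precedence over unscheduled ones. A Week 26 abnormality that has normalised by Week 52, or an unscheduled abnormality displaced by a scheduled result, is therefore shown as no shift. Displaced unscheduled values also drop out of the by-visit statistics. Listings and, for some results, the AESI table still carry them, but no table says how many subjects had any on-treatment out-of-range value.

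The size cannot be derived from the SAP. The range of 0% to about half of ever-abnormal subjects assumes equal prevalence at the two visits, two samples per subject and, at the upper end, independence and low prevalence. If abnormalities were more frequent at Week 26 than at Week 52 the share could be larger; in the reverse case it would be smaller. Displaced unscheduled abnormalities would add to it by an unknown amount. This is an inexpensive improvement that serves the primary objective, not a flaw that invalidates the planned tables.

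**What to change.** In SAP 7.5.4 and the section 9 table list, add:

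- for hematology and blood chemistry, a shift from baseline to the worst post-baseline value, with the highest and the lowest value tabulated separately;
- for urinalysis, a shift from baseline to the worst post-baseline category.

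State that these tables use all on-treatment results, scheduled and unscheduled. Keep the baseline-to-last shift, and keep the scheduled-first rules in 7.9 for that table and for the by-visit statistics.

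The cost is one extra table per panel, with no new data. Abnormality rates will look less favourable than in the last-visit table and will rise with the number of samples a subject contributes. A footnote giving the number of post-baseline samples per subject would help the reader allow for that.

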7.6 Vital Signs and Physical Exam

The descriptive statistics for Vital Signs collected at each visit and changes from Baseline will be provided. Nominal eCRF visit will be used as analysis visit.

Physical exam will be provided in a subject-by-subject listing.

7.7 Pharmacokinetic Analysis

Quantifiable PK profiles of CD5789 from previous PK studies 18237 and 40182 were used to investigate the relationship between AUC_{0-24h} and selected plasma points. A strong correlation was found between AUC_{0-24h} and C_{4h} using linear regression. The extrapolated AUC_{0-24h} will be calculated using the following equation. For more details, refer to the document *CD5789 Limited sampling strategy for estimation of the AUC_{0-24h} in the 9 to 11 years old subjects*.

$$AUC_{0-24h} = 34.26 + 7.90 * C_{4h}$$

The PK parameters C_{4h} and extrapolated AUC_{0-24h} will be summarized by descriptive statistics. Coefficient of variation (CV), geometric mean (GEO Mean), geometric standard deviation (GEO SD) and geometric coefficient of variation (GEO CV) will be presented as well.

For C_{4h} , the BLQ (below limit of quantification) values will be imputed using the LOQ (limit of quantification: 5pg/mL). Summaries with imputation and with no imputation will be both provided.

7.8 Other analyses (quality of life Questionnaire)

The DLQI/ C-DLQI will be summarized descriptively. Only SAF subjects with both baseline and post-baseline visit assessments using the same age-appropriate questionnaire will be included in the analyses.

Total Scores and Change from Baseline at Week 12, 26, and 52/Early Termination for DLQI/C-DLQI, DLQI only, and C-DLQI only will be summarized. In addition, number and percent of subjects will be reported for each of the following categories of the effect of disease on the quality of life as specified in Table 1:

Table 1 DLQI/C-DLQI Categories

DLQI		C-DLQI	
DLQI Category	Range of Total Score	C-DLQI Category	Score Maximum
No effect	0 - 1	No effect	0 - 1
Small effect	2 - 5	Small effect	2 - 6
Moderate effect	6 - 10	Moderate effect	7 - 12
Very large effect	11 - 20	Very large effect	13 - 18
Extremely large effect	21 - 30	Extremely large effect	19 - 30

Summaries of DLQI only and C-DLQI only by each dimension as defined in Table 2 below will also be provided.

Table 2 DLQI/C-DLQI Dimensions

DLQI		C-DLQI	
DLQI dimensions	Score Maximum	C-DLQI dimensions	Score Maximum
Total Score	30	Total Score	30
Symptoms and feelings	6	Symptoms and feelings	6
Daily Activities	6	Sleep	3
Leisure	6	Leisure	9
Work and School	3	School or holidays	3
Personal relationships	6	Personal relationships	6
Treatment	3	Treatment	3

7.9 Analysis visit definition

For efficacy, DLQI/ C-DLQI and local tolerability data, analysis visit will be assigned according to the algorithm in Table 3 below to summarize the data by proper visit window interval. Study day is calculated as visit date minus the date of first application plus 1. If multiple measurements are taken in the same interval, the one closest to the target study day will be used for the analysis. If two measurements are taken with equal differences in timing compared with the target date, the nominal visit number (recorded on the CRF page) will be used. If there is missing measurement at Baseline, Screening data will be used to impute the missing baseline data, i.e. Baseline will be the last available data prior to first application of study drug.

Table 3 Analysis Visit and Visit Window

Analysis Visit	Analysis Visit Number in Derived Dataset	Target Study Day	Visit Window (Study Day)
Baseline	1	1	[≤1]
Week 1	2	8	[2 – 11]
Week 2	3	15	[12 – 21]
Week 4	4	29	[22 – 42]
Week 8	5	57	[43 – 70]
Week 12	6	85	[71 – 112]
Week 20	7	141	[113 – 161]
Week 26	8	183	[162 – 224]
Week 38	9	267	[225 – 315]
Week 52	10	365	> 315

When assigning the analysis visits for vital signs, no visit window will be applied; Nominal eCRF visit will be used as analysis visit for summaries. Only data from schedule visit will be summarized.

When assigning the analysis visits for laboratory data, no visit window will be applied, however, the following rules will be applied:

1. If sample date is at or prior to date of first application, the data will be considered as screening visit. If multiple measurements of screening due to rescreening, retest or other unexpected reasons, the data closest to date of first application will be chosen.
2. Lab data from scheduled visit will be considered first when assigning analysis visit of each scheduled visit. If there is no data from scheduled visit available, the last of those corresponding unscheduled visit will be considered for assignment of analysis visits.
3. When assigning Final visit, the lab data from the last post-baseline scheduled visit during treatment period will be considered first. If the last scheduled visit during treatment period have missing lab data due to any reason and there are subsequent unscheduled lab data available, the last of those corresponding unscheduled lab data will be assigned as Final visit. Otherwise, the previous visit lab data will be considered in the same manner.

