3.1.2 PGA (Physician Global Assessment) of truncal acne

The areas defined PGA assessment are shoulders, upper back and anterior chest which are accessible to self-application by the subject, i.e. the regions that the subject can easily reach and apply the study drug by himself or herself. PGA will be confined to a global assessment. The PGA is a snapshot static assessment.

Investigators will evaluate the upper truncal acne at Screening, Baseline, and Weeks 12, Week 20, Week 26, Week 38 and Week 52/ET visits or any unscheduled visit, according to the following scale.

Physician Global Assessment Scale (PGA) Trunk		
0	Clear	Clear skin with no inflammatory or non-inflammatory lesions.
1	Almost Clear	A few scattered comedones and a few small papules.
2	Mild	Easily recognizable; less than half the surface is involved. Some comedones and some papules and pustules.
3	Moderate	More than half of the surface is involved. Many comedones, papules and pustules. One nodule may be present.
4	Severe	Entire surface is involved. Covered with comedones, numerous papules and pustules. Few nodules may or not be present.

Specific requirements for children between 9 and 11 years old who do not have moderate acne on the upper truncal region at Baseline (i.e. who do not have PGA of 3, at least 20 inflammatory lesions on the trunk and at least 20 non-inflammatory lesions on the trunk):

The PGA scale will be completed at all visits (including Week 1, 2, 4 and 8 visits), and used by the investigators to decide if they want to start the treatment for truncal acne. However, the PGA data from these subjects will not be analyzed.

Note: PGA assessment is to be done prior to lesion counts.

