3.2.1 Local tolerability assessment

Local tolerability (erythema, scaling, dryness, and stinging/burning) will be assessed on the face (forehead, each cheek, nose, chin) and trunk (upper trunk; middle and lower trunk will be captured if subject applied study drug on these areas) separately and will be graded separately at Baseline and at each post-baseline visit. Refer to protocol section 7.2.3 and 7.2.4 for more details.

Specific requirements for children between 9 and 11 years old who do not have moderate acne on the trunk at Baseline (i.e. do not have PGA of 3, at least 20 inflammatory lesions on the trunk and at least 20 non-inflammatory lesions on the trunk):

If the investigators decide to start the treatment for truncal acne in these subjects during the study, then the local tolerability scales (for trunk) will be completed and data will be evaluated in the safety analysis.

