5.2 Safety (SAFT) Population on the Trunk

The SAFT population is defined as any subjects in the SAF population who also applied the study medication on the upper truncal region and /or on the middle and lower back at least once.

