7 STATISTICAL METHODS AND DATA CONSIDERATIONS

For statistical analyses purpose, baseline is defined as the last measurement prior to the first application of the study drug.

No inferential statistical analysis is planned. Data to be collected will be summarized as observed.

For the summary statistics, the categorical variables will be summarized by frequency and percentage for each response category (N, %); and the continuous variables will be summarized using means, medians, minimum, maximum, and standard deviations.

All efficacy variables, DLQI/ C-DLQI, local tolerability, laboratory tests and vital signs will be summarized and analyzed by analysis visit. The methodology for defining analysis visit is provided in Section 7.9 “Analysis visit definition”.

SAS version 9.3 or above will be used for all statistical analyses.

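### Trunk tolerability has no trunk-specific baseline: in children aged 9-11 who start trunk treatment after the face, scores taken before the first trunk application are classed as post-baseline

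*SAP*

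**What the plan says.** **Baseline and study day.** Section 7 states that "baseline is defined as the last measurement prior to the first application of the study drug". Section 7.9 repeats the rule ("Baseline will be the last available data prior to first application of study drug") and counts time from the same date: "Study day is calculated as visit date minus the date of first application plus 1". Table 3 expressly covers local tolerability, and its Baseline window ends at study day 1. No separate date is given for the trunk. The only place that separates the two areas is treatment duration (Section 7.5.1.2), which takes the earlier of the face and trunk starts.

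**Late trunk start.** For children aged 9-11 without moderate truncal acne at Baseline, Section 3.1.2 has the PGA completed at all visits and "used by the investigators to decide if they want to start the treatment for truncal acne". If they start, Section 3.2.1 says "then the local tolerability scales (for trunk) will be completed and data will be evaluated in the safety analysis". The general sentence of the same section says that face and trunk tolerability "will be graded separately at Baseline and at each post-baseline visit".

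**Analysis.** SAFT (Section 5.2) takes in any SAF subject "who also applied the study medication on the upper truncal region and /or on the middle and lower back at least once", so late starters belong to it. Section 7.5.2 analyses trunk tolerability in SAFT and says that "the number and percentage of subjects with a local tolerability score worsened from baseline will be summarized descriptively at each post-baseline visit", and also for the Final and Worst scores. It sets no condition that both a baseline and a later score be present. Sections 7.4.3, 7.5.4 and 7.8 do set that condition for their own analyses.

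**The concern.** For most subjects face and trunk treatment start together, and one anchor date serves both. For a child who starts the trunk later, the anchor is the face start. The score that best describes the trunk before treatment, one taken shortly before the first trunk application, then falls after the anchor. The rule treats it as an on-study result and not as the reference value.

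Two consequences follow for a named safety endpoint (Section 4.2). Scores on an untreated trunk can enter the post-baseline summaries. And if such a child has no trunk score from before the face start, it is not fixed whether the child counts in the denominator of the worsening percentage. A child kept there could never count as worsened, which would pull the percentage down. All late starters fall in the under-18 stratum of the age subgroup that Section 7.5.2 plans.

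**Working it through.** The SAP gives no figure on this point to reproduce. The check applies its rules to a late trunk start.

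**Inputs from the SAP**
- Target study days of the nine post-baseline visits (Table 3): 8, 15, 29, 57, 85, 141, 183, 267, 365.
- Windows (Table 3): Baseline up to day 1; Week 4, days 22-42; Week 12, days 71-112; Week 26, days 162-224.
- Planned enrolment: 450 (Section 6), taken as the upper limit for SAFT.

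**Assumptions**
- Trunk treatment starts at the Week 4, 12 or 26 visit, and the trunk is scored at that visit before the first trunk application.
- k late starters lack a trunk baseline (k = 5, 10, 20).
- 20% worsen among subjects with both scores.
- The under-18 subgroup of SAFT has 225 subjects.

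**Step 1: where the pre-application trunk score lands.** A score on day 29, 85 or 183 falls in the Week 4, 12 or 26 window. None can fall in the Baseline window. The Screening fallback in Section 7.9 does not help, because it too looks only before the first application of study drug.

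**Step 2: two readings of Section 3.2.1**

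*Reading A: the trunk is scored only once trunk treatment is started.* This is the more natural reading of the specific rule for these children. No trunk score exists from before the face start, so there is no baseline under the rule.

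| Trunk start | Trunk scores from start visit on | Of these, on an untreated trunk | Baseline under the rule |
|---|---|---|---|
| Week 4 (day 29) | 7 | 1 | none |
| Week 12 (day 85) | 5 | 1 | none |
| Week 26 (day 183) | 3 | 1 | none |

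*Reading B: the trunk is scored at every visit, as in the general sentence.* A study-entry baseline exists and worsening is counted against it.

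| Trunk start | Age of baseline at trunk start | Post-baseline scores on an untreated trunk |
|---|---|---|
| Week 4 | 29 - 1 = 28 days | 3 of 9 (days 8, 15, 29) |
| Week 12 | 85 - 1 = 84 days | 5 of 9 (adding days 57, 85) |
| Week 26 | 183 - 1 = 182 days | 7 of 9 (adding days 141, 183) |

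**Step 3: the denominator.** This arises where a trunk baseline is missing, as under Reading A. If the k late starters stay in a denominator of N but cannot count as worsened, then

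reported % = 20% × (1 - k/N).

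| N | k = 5 | k = 10 | k = 20 |
|---|---|---|---|
| 450 | 20 × 445/450 = 19.8% | 20 × 440/450 = 19.6% | 20 × 430/450 = 19.1% |
| 225 | 20 × 220/225 = 19.6% | 20 × 215/225 = 19.1% | 20 × 205/225 = 18.2% |

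The largest drops are 20 - 19.1 = 0.9 points overall and 20 - 18.2 = 1.8 points in the subgroup.

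**The case against.** **The anchor does not cause the missing baseline.** A reader might infer that the single anchor leaves these children without a trunk baseline. Under Reading A the cause is the collection rule in Section 3.2.1: nothing is scored on the trunk before the face start. The anchor does harm only if a trunk score is taken between the face start and the first trunk application. The SAP does not say that one is, and it refers to protocol Sections 7.2.3 and 7.2.4, which are not shown. This objection stands, so the point is conditional on what is collected. The protocol's collection rules would not by themselves change how the SAP classes such a score if there is one.

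**Worsening is not always lost.** A reader might also infer that trunk worsening can never be counted in late starters, even with a score from before trunk treatment. That is wrong under Reading B, where the study-entry score is the baseline. A baseline before any study drug is a uniform and usable rule. What remains under Reading B is that scores on an untreated trunk are summarised as post-baseline.

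**The denominator may already be the right one.** Section 7 says data are summarised as observed, and Section 7.4.6.1, placed under efficacy, rules out imputation. A subject without a baseline has no observed worsening status. Where the SAP wants the whole population as denominator, as for IGA success in Section 7.4.1, it says so. This makes the diluted percentage the less likely outcome. It does not exclude it, because Section 7.5.2 bases the analysis on SAFT and omits the condition stated in three other sections.

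**The damage is limited.** The tables are descriptive. Trunk scores after trunk start still enter Worst and Final, a misplaced pre-application score can only raise Worst or leave it unchanged, adverse event tables are unaffected, and local tolerability is listed by subject. All of this stands. A larger distortion within ages 9-11 alone is not a planned result, since Section 7.5.2 splits tolerability only at 18 years.

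**Conclusion.** The concern holds in a conditional and minor form. The baseline and study-day rules make no provision for a trunk start later than the face start, although the SAP allows one and brings those children into SAFT. Any trunk score taken between the two starts is classed as post-baseline. Whether such scores are recorded, and whether a study-entry trunk score exists, depends on protocol sections not shown. Separately, Section 7.5.2 leaves open whether SAFT subjects without a trunk baseline remain in the denominator for worsening.

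The effect reaches only late trunk starters, whose number the SAP does not give. On the assumed inputs, the denominator question moves the percentage by at most about 1 point overall and 2 points in the under-18 subgroup. The 20%, the 225 and the values of k are all assumptions; a higher share of late starters would give a proportionally larger drop. The documents do not support a claim that trunk worsening is systematically missed or that the reported percentage will be diluted.

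**What to change.** Add to Sections 7.5.2 and 7.9, for trunk tolerability in SAFT only:

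1. Baseline is the last trunk score before the first trunk application.
2. Only trunk scores after that application are post-baseline, including for Worst and Final.
3. The number and percentage worsened are based on subjects with a trunk baseline and a post-baseline trunk score, as Sections 7.4.3, 7.5.4 and 7.8 already require for their own analyses. Print n in each row.

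Results do not change for subjects who start face and trunk together and have both scores. The cost is a few lines of text and a second anchor date, the first trunk application, in the derived data. Late starters without a trunk score before that date drop out of the worsening percentage; the printed n makes this visible. The change concerns analysis only and leaves the treatment rules as they are.
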